7.12. Limitations of the research methods

Randomised controlled trials are important and powerful tools in assessing efficacy and safety but have their limitations in terms of generalisability. In order to assess health economics, clinical effectiveness and safety of Tofacitinib in a usual care setting, parameters need to be determined by performing observational studies.

Inherent limitations of non-interventional, observational, non-controlled, non-randomised studies in general are the risk of selection/ascertainment bias and some lack of a parallel control group, which complicate the interpretation of the causality between treatment and outcomes. Furthermore, as with any "as observed" analysis, there is a potential risk of bias due to missing outcome data; the risk increases with increasing number of missing outcome data.

As data captured will be limited to information available from the physician participating in the study under a usual care setting, there is a greater possibility that there will be individual items of missing data (e.g. CRP not measured or FFbH questionnaire not completed). Following up patients after treatment escalation, rather than discontinuing patients from the study when they switch from Tofacitinib, should result in a higher proportion of the patients remaining in the study until the planned completion date. Where data are missing, information from the patient at other visits may be used in the primary analysis model to assess predictors of treatment decisions. If the different factors being considered in the primary statistical model to look at impact of treatment change are highly correlated it may not be clear which of the factors is in fact driving the rate of treatment escalation. Other sensitivity analyses may be explored to assess the impact of any confounding. Further details will be included in the SAP.

Patients selected for study inclusion represent a population who are initiated on Tofacitinib as part of a usual care setting. The sample of patients will be obtained from physicians who are willing to participate in the study and there is a possibility that certain types of patients will be selected to be prescribed Tofacitinib (selection bias) and join the study and this could potentially have an impact on findings of the primary analysis (if the 'type' is expected to impact the rate of treatment escalation). Therefore, study findings may not be generalizable to all RA patients.

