3.1 STUDY DESIGN

This is a 60-month, prospective, non-interventional, multi-centre study to evaluate the impact of the following factors on the number of treatment escalations of tofacitinib patients in 24 months.

Eligible patients will be followed up from the date of first tofacitinib prescription for 24 months. Patients who are switched from the initial tofacitinib therapy to other therapies will also be followed up to 24 months. Patient documentation is expected quarterly as per standard clinical practice.

This study observes drug prescription and follow-up visits in daily medical care. Therapeutic strategies and frequency of patient follow-up are decided by the treating physician.

Figure 1. Study Design

The planned recruitment period is 36 months. With planned observation duration of 24 months per patient, the entire study would thus last for 60 months. The study started in October 2017 and, due to an extension of the recruitment period of 9 months, the study will end in July 2023. Overall, about 1500 patients in about 200 centres in Germany are to be included in this non-interventional study.

The schedule of activities table provides an overview of the visits that may be documented. Refer to the STUDY PROCEDURES and ASSESSMENTS sections of the protocol for detailed information on each documentation and assessment.

According to his clinical practice the HCP may schedule visits (unplanned visits) in addition to those listed on the schedule of activities, in order to conduct evaluations or assessments required to protect the well-being of the patient. As this is a non-interventional study none of these visits are mandatory and every visit should be scheduled according to clinical practice.

Table 1. Schedule of Activities

Study Week	Baseline (Enrolment)	Month 3	Month 6	Month 9	Month 12	Month 15	Month 18	Month 21	Month 24
Visit Number	1	2	3	4	5	6	7	8	9
Info1med Consent	x								
Initial dia21osis of RA	x								
Proimostic factors	x								
Relevant comorbidities	x								
Demographic data	x								
Insurance type	x								
Smoking history and cwTent smoking status	x								
Phvsical Examination (weight, height)	x								
Inclusion/Exclusion criteria	x								
Varicella vaccination status	x								
Prior drug treatment of RA	x								
RA-treatment with tofacitinib and/or other DMARDs	x	x	x	x	x	x	x	x	x
Concomitant treatment of RA with Glucocorticoids	x	x	x	x	x	x	x	x	x
InflammatoIY Markers	x	x	x	x	x	x	x	x	x
Documentation of AE	x	x	x	x	x	x	x	x	x

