6.3 SECONDARY FULL ANALYSIS SET

Patients with data collected while taking tofacitinib will be assigned to the Secondary Full Analysis Set (SFAS) at a given time point, which will be used for all secondary endpoint analyses. A patient is considered on tofacitinib at a given timepoint if the patient has not terminated or paused tofacitinib at the time of the visit or event. Termination or pauses are documented in eCRF instrument “Rheumatologische Medikation” for therapy class tsDMARD/bDMARD, where variable *Change* (BDCM.CHANGECD) is set to “Therapy stop” = termination or set to “Therapy paused” = pause.

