9.2.3.2 RATE OF LDA

Each definition of LDA (Section 7.1.2.2) will be presented as in Section 9.1.4, using the SFAS, only including data when patients were taking tofacitinib. Missing data will not be imputed (as per Section 8.2).

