12 APPENDICES

12.1 APPENDIX 1: DATA DERIVATION DETAILS

12.1.1 A1.1 DEFINITION AND USE OF VISIT WINDOWS IN REPORTING

Visit windows will be used for efficacy variables, and for any safety displays that display by month. The visit windows for the analysis defined in the table differ from that outlined in the protocol. The analysis visit windows will be M1, M3±14 days, all subsequent visits MX ± 28 days.

Table 11.1: Visit windows

Visit Label	Target Day	Definition [Day window]
Enrolment	1	1
Month 3	91	77 to 105
Month 6	182	154 to 210
Month 9	273	245 to 301
Month 12	365	337 to 393
Month15	456	428 to 484
Month18	547	519 to 575
Month 21	638	610 to 666
Month 24	730	702 to 758

For the lab values, if the calculated study day for the labelled baseline visit is not study Day 1, but falls within 40 days before the start of the study dosing, then that data should be used for the baseline instead of leaving baseline missing.

For the other values, if the calculated study day for the labelled baseline visit is not study Day 1, but falls before the start of the study dosing, then that data should be used for the baseline instead of leaving baseline missing.

If baseline is missing there will be no imputation and although the subject's data will be included in summary data it will not be included in any change from baseline analyses.

If two or more visits fall into the same window, keep the one closest to the Target Day. If two visits are equal distance from the Target Day in absolute value, the later visit should be used.

For the primary endpoint analysis, escalations occurring in-between two planned visits will be assigned to visits using the visit windows described above. If two or more escalations

fall into the same window, all escalations will be counted. Escalations, which are assigned to the baseline visit, will be counted under the Month 3 Visit, unless the escalation occurred before first tofacitinib treatment. Escalations, which fall outside the visit windows, will be assigned to the visit nearest to the Target Day. If two visits are equal distance from the escalation date in absolute value, the later visit should be used.

(Safety analysis may follow Pfizer standard)

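### SAP 12.1.1 keeps the visit closest to the target day without requiring that it holds the measurement, so a collected value can be lost from the by-month secondary tables

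*SAP*

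**What the plan says.** SAP 12.1.1 sets the scope: "Visit windows will be used for efficacy variables, and for any safety displays that display by month". The widths are "M3±14 days, all subsequent visits MX ± 28 days". For several visits in one window the instruction is "If two or more visits fall into the same window, keep the one closest to the Target Day", with the tie rule "If two visits are equal distance from the Target Day in absolute value, the later visit should be used". Neither sentence mentions whether the visit contains the variable or whether the patient is still on tofacitinib.

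The documents foresee both ingredients of the problem. On extra visits, SAP 3.1 says that "the HCP may schedule visits (unplanned visits) in addition to those listed on the schedule of activities". On incomplete visits, protocol 7.12 expects "individual items of missing data (e.g. CRP not measured or FFbH questionnaire not completed").

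The secondary summaries then add two restrictions. SAP 9.2.3.2 (LDA) is typical: "using the SFAS, only including data when patients were taking tofacitinib. Missing data will not be imputed". Treatment status is defined in SAP 6.3: "A patient is considered on tofacitinib at a given timepoint if the patient has not terminated or paused tofacitinib at the time of the visit". SAP 9.1.4 uses non-missing values as the denominator for percentages. SAP 8.2 and 8.3 and the summary table in 9.2.6 confirm that the secondary endpoints are not imputed.

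**The concern.** The tables need a value for each endpoint in each window, but the rule chooses a visit. If the chosen visit lacks the endpoint, the patient counts as missing for that month although a valid value was collected inside the window. No later step in the secondary analyses recovers it. The summaries exposed are LDA, remission, functional remission, and change from baseline in DAS28, morning stiffness, FFbH, EQ-5D and FACIT-Fatigue.

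The same rule meets the on-tofacitinib restriction without a stated order. Two programmers could follow the SAP faithfully and produce different monthly tables for patients who stop within a window.

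**Working it through.** **1. The windows.** Target day ±14 for Month 3 gives 91 ± 14 = 77 to 105, which is 29 days. Target day ±28 for Month 6 gives 182 ± 28 = 154 to 210, which is 57 days. All eight post-baseline windows in the SAP table reproduce this way. Two visits up to 56 days apart can therefore share a window from Month 6 on.

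**2. Missing measurement (visit days assumed).** Month 6, target day 182. An unplanned visit on day 180 has no ESR; a complete visit takes place on day 200.
- Distances: |180 − 182| = 2 and |200 − 182| = 18.
- As written, day 180 is kept and DAS28-4 (ESR) is missing at Month 6.
- Choosing among visits with a non-missing value keeps day 200.

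FFbH and EQ-5D are less exposed. Their scoring rules tolerate missing items, so the loss arises mainly when the whole questionnaire is absent.

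**3. On-drug restriction (visit days assumed).** An on-drug visit on day 160 is 22 days from target. A visit on day 190, after the stop, is 8 days from target.
- Select, then restrict: day 190 is kept and then excluded, so there is no Month 6 value.
- Restrict, then select: day 160 is kept.

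To see how often the order matters, take every pair of days in a window with the earlier visit on drug and the later one off drug.
- Months 6–24: there are 57 × 56 / 2 = 1596 pairs. The off-drug visit is at least as close when the on-drug visit lies k days before target and the later one falls in the next 2k days. That gives the sum of 2k for k = 1 to 28 = 812, or 50.9%.
- Month 3: 29 × 28 / 2 = 406 pairs; the sum of 2k for k = 1 to 14 = 210, or 51.7%.
- With the restriction first, the count is 0.

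These are counts of possible day pairs, not estimates of how often such pairs occur.

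**4. Illustrative size for LDA.** No input here comes from the documents. Let d be the share of patient-windows with two visits, m the share of those in which the usable value is lost, p1 the LDA rate in the rest, and p2 the rate in the double-visit group. The lost values are taken as typical of that group.
- Lost share = d × m
- Rate from all collected values = (1 − d) × p1 + d × p2
- Reported rate = [(1 − d) × p1 + d × (1 − m) × p2] / (1 − d × m)

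With p1 = 40% and p2 = 20%:

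| d | m | Lost share | All collected | Reported | Shift (points) |
|---|---|---|---|---|---|
| 10% | 30% | 3% | 38.0% | 38.6% | +0.6 |
| 10% | 50% | 5% | 38.0% | 38.9% | +0.9 |
| 20% | 30% | 6% | 36.0% | 37.0% | +1.0 |
| 20% | 50% | 10% | 36.0% | 37.8% | +1.8 |

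The shift equals d × m × (1 − d) × (p1 − p2) / (1 − d × m). It is zero when p1 = p2 and changes sign when the rates are swapped. With p1 = 20%, p2 = 40% and d = 10%, the rate from all collected values is 22.0%, and the reported rate is 0.208 / 0.97 = 21.4% (m = 30%) or 0.200 / 0.95 = 21.1% (m = 50%).

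**The case against.** **The windows may be meant per variable.** SAP 12.1.1 opens by applying windows to efficacy variables. Its baseline rules distinguish laboratory from other values and are meant to avoid leaving baseline missing. That supports a per-variable reading, and the text does not exclude it. But the sentence on several visits speaks of visits, and the SAP does not state the other reading. Where it wants available values sought out, as for the primary-model covariates in 8.1, it says so.

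**Off-drug visits may never be candidates.** A reader might infer that the plan keeps an off-tofacitinib visit and then excludes it. The documents do not say that. SAP 6.3 assigns data to the SFAS by time point, and 9.2.3 admits only data collected on tofacitinib. Both are most naturally read as removing off-drug data first, and then nothing is lost. What stands is that the order is not written down.

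**The bias may not exist.** A reader might also infer that the loss makes LDA and remission look better. Extra visits are described as serving the patient's well-being, so clustering in patients doing badly is plausible, but neither document says so or gives a rate of double visits. Documentation is expected quarterly, so a second visit in a window would usually be an unplanned or irregular one. The direction in the table above comes entirely from the assumed LDA rates.

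**The effect is small and the tables are descriptive.** For a rate of 38% and the planned 1500 patients, the 95% half-width is 1.96 × √(0.38 × 0.62 / 1500) = 2.5 points, and wider with fewer patients on drug. Protocol 7.12 already acknowledges bias from missing data. This limits the importance of the point but does not justify discarding collected values.

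**One visit per window keeps a patient's values on the same day.** That is a real advantage, and the fix gives up part of it.

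**Conclusion.** The point holds for the missing measurement: followed as written, the rule lets a nearer incomplete visit replace a complete one, and the secondary analyses have no step that restores the value. For treatment status it holds only as an unspecified order of operations; a loss there is possible under one order and absent under the other.

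The scope is the windowed by-month secondary summaries. The PPAS repeat of the primary model may also be touched, since SAP 9.2.6 states no imputation for it, but SAP 6.5 limits that set to scheduled visits, so two scheduled visits would have to share a window. The primary FAS analysis keeps all visits and fills missing covariates with the nearest available value. Time to first escalation and drug survival use event dates.

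Frequency and direction cannot be derived from the documents. The shifts in the illustration rest on assumed inputs, and its m pools missing and off-drug losses; if off-drug visits are removed first, only the missing-measurement part remains. This is a minor improvement to the plan, not a threat to its conclusions.

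**What to change.** Replace the sentence on several visits in SAP 12.1.1 with a rule of this kind: within a window, for each endpoint, use the assessment closest to the Target Day among visits with a non-missing value; for endpoints restricted to on-tofacitinib data, consider only visits on tofacitinib; ties go to the later visit. Take all components of a composite score (DAS28, SDAI, CDAI, Boolean remission) from the same visit.

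Exempt the satisfaction table from the on-drug filter explicitly. SAP 7.1.2.11 and 9.2.3.11 deliberately show patients who stop at Visit X, while the opening of 9.2.3 places all secondary endpoints in the SFAS.

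The cost is a few sentences and a reordering of the selection steps before database lock; no new data are needed. Different endpoints for one patient may then come from different days within a window. The interim analyses are stated to use the same methods as the final one, so the report should say which selection order they used if the final tables differ.

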7. RESEARCH METHODS

7.1. Study design

This is a 60-month, prospective, non-interventional, multi-centre study to evaluate the impact of the following factors on the number of treatment escalations of Tofacitinib patients in 24 months.

[figure not shown]
Eligible patients will be followed up from the date of first Tofacitinib prescription for 24 months. Patients who are switched from the initial Tofacitinib therapy to other therapies will also be followed up to 24 months. Patient documentation is expected quarterly as per standard clinical practice.

This study observes drug prescription and follow-up visits in daily medical care. Therapeutic strategies and frequency of patient follow-up are decided by the treating physician.

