3.2.1 TREATMENT/COHORT LABELS

For the primary analysis, the number and timing of treatment escalations of tofacitinib patients in 24 months will be presented (see Section 7.1.1). The treatment labels for other analyses are presented below:

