7 ENDPOINTS AND COVARIATES

7.1 EFFICACY/ EFFECTIVENESS ENDPOINT(S)

7.1.1 PRIMARY ENDPOINTS

Number and timing of treatment escalations of tofacitinib patients in 24 months, where Treatment Escalation in this study is defined as a switch to another DMARD or combination of DMARDs when compared to the last visit.

The following types of escalations will be distinguished:

1. Treatment **Termination**, which is the termination of a DMARD (or multiple when on combination therapy) without starting a new DMARD therapy. Premature study terminations (without documented treatment termination) will not be considered treatment terminations.
2. Treatment **Step-up** which is an increase from the current treatment regime towards e.g. a combination of DMARDs
3. Treatment **Step-down**, which is a de-escalation from the current treatment regime, e.g. from combination therapy to monotherapy

Patients start their therapy at baseline with tofacitinib either in Monotherapy or in Combination therapy with MTX. Subsequent therapy changes are documented on eCRF instrument “Rheumatologische Medikation“ by:

- adding additional DMARDs on top of the current therapy
- stopping the current DMARD in monotherapy and adding a new DMARD
- stopping one of multiple DMARDs when on combination therapy
- stopping one of multiple DMARDs when on combination therapy and adding a new DMARD
- stopping all DMARDs and not starting a new therapy. The escalation types depend on the combination of DMARD classes (tsDMARD vs bDMARD vs TNFi vs csDMARD). The eCRF does not explicitly distinguish between tsDMARD vs bDMARD vs TNFi, but combines all rheumatic medications belonging to the above classes under

tsDMARD/bDMARD. For the definition of treatment escalations, the following assignment of rheumatic medication to DMARD classes will be done:

tsDMARDs:

- baricitinib
- upadacitinib
- filgotinib

TNFi:

- etanercept
- adalimumab
- certolizumab
- golimumab
- infliximab

bDMARDs (excluding TNFi):

- abatacept
- rituximab
- anakinra
- tocilizumab
- sarilumab

For details of treatment escalations, e.g., which DMARD class addition or reduction leads to a particular escalation type, see table 12.2 in section 12.1.2.

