9.1.1 ANALYSIS FOR RECURRENT EVENT DATA

In order to account for the possibility that there are multiple events occurring for each patient cox-proportional hazards modeling will be used with adjustment for recurrent events. This involves fitting either the Andersen and Gill or Prentice, Williams and Peterson gap-time models to the data.

For each patient, the data will be split into time periods, then data for each time window should include the patient's status, the time of event (if the event occurred) and the value of each of the factors of interest:

So, for patient A, who had events at M6 and M18, their data could look like this:

Patient	Start	Stop	Treatment Escalation Status	Factor A	Factor B	Factor C
A	0	M6	1	3.9	0.6	-10
A	M6	M12	0	3.0	1.5	-20
A	M12	M8	1	2.8	1.7	-10
A	M18	M24	0	2.2	2.3	-10

The cox proportional hazards model (using PROC PHREG) is then used, including the factors of interest (Section 7.3.1) to determine which, if any of them, have an impact on the rate at which treatment changes occur.

Any potential confounders should be included in the model also (Section 7.3.3).

The estimated event rate will be presented, along with 95% confidence interval and p-value, for each of the covariates of interest. Note: These will not be presented for the variables considered to be confounders.

The number and proportion of people experiencing an event at each time point will be presented.

Supportive tables will also be presented which summarises each of the covariates in the model at each visit.

The analysis will be performed for each type of escalation as defined in section 7.1.1 and overall.

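### In the by-visit escalation table, Month 3 collects 135 days of escalations, Months 6 to 21 collect 91 or 92 each, and Month 24 about 47, so a constant escalation rate would show a false high at the first visit and a false low at the last

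*SAP*

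**What the plan says.** SAP 7.1.1 makes both the number and the timing of escalations the primary endpoint, and SAP 3.2.1 says that "the number and timing of treatment escalations of tofacitinib patients in 24 months will be presented". For the recurrent-event analysis, SAP 9.1.1 adds a descriptive table: "The number and proportion of people experiencing an event at each time point will be presented".

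SAP 9.2.2 and 12.1.1 state how a between-visit escalation reaches a time point:

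- Windows come first: "The analysis visit windows will be M1, M3±14 days, all subsequent visits MX ± 28 days".
- Dates outside every window follow the nearest-visit rule: "Escalations, which fall outside the visit windows, will be assigned to the visit nearest to the Target Day".
- Ties go forward: "If two visits are equal distance from the escalation date in absolute value, the later visit should be used".
- Baseline is emptied into the next visit: "Escalations, which are assigned to the baseline visit, will be counted under the Month 3 Visit, unless the escalation occurred before first tofacitinib treatment".

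All escalations that fall in one window are counted. We found no adjustment for the number of days that each visit represents. SAP section 2 explains the choice: the assignment was mostly aligned with that of the secondary endpoints, for consistency and greater precision.

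**The concern.** Nearest-visit assignment suits a measurement taken at about the visit date. An escalation is an event that can occur on any day, so a visit's count depends on how many days the rule sends to it. An interior visit receives half of the interval on each side. Month 3 receives the whole interval before it and half of the one after it. Month 24 receives half of the interval before it and whatever observation follows its target day.

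The by-time-point table is where a reader looks for the timing of escalations. If its time points stand for unequal amounts of time, a high first column and a low last column can arise with no change in prescribing. They could be read as early switching followed by a late fall.

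**Working it through.** **Inputs.** Target days 1, 91, 182, 273, 365, 456, 547, 638 and 730, and the windows, are from the SAP 12.1.1 visit table. Follow-up is from Protocol 7.1: "Eligible patients will be followed up from the date of first Tofacitinib prescription for 24 months". It is taken to end on day 730, the Month 24 target day, and then varied.

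**Check of the plan's own figures.** Target day ± 14 for Month 3 and ± 28 for later visits reproduces all eight post-baseline windows (for example 91 ± 14 = 77 to 105, and 730 ± 28 = 702 to 758). Of days 2 to 730, 329 of 729 lie outside every window, so the nearest-visit rule decides 45% of the days.

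**Catchment per visit.** Every window lies inside its own nearest-target zone, so the combined rule amounts to nearest target day. The boundaries are midpoints between target days. The ties at days 46, 319 and 684 go to the later visit.

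| Visit | Days collected | Number |
|---|---|---|
| Month 3 | 2–45 (from baseline) and 46–136 | 44 + 91 = 135 |
| Month 6 | 137–227 | 91 |
| Month 9 | 228–318 | 91 |
| Month 12 | 319–410 | 92 |
| Month 15 | 411–501 | 91 |
| Month 18 | 502–592 | 91 |
| Month 21 | 593–683 | 91 |
| Month 24 | 684–730 | 47 |

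Month 24 has 19 days if the last visit is on day 702 and 75 if dates run to day 758. It is below 91 in each case. The Month 3 figure does not depend on this.

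**Event counts at a constant rate, all days equally likely.** Month 3/Month 6 = 135/91 = 1.48. Month 24/Month 6 = 47/91 = 0.52 (19/91 = 0.21; 75/91 = 0.82). Month 3/Month 24 = 135/47 = 2.87 (135/75 = 1.80).

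**People with at least one event.** This is what SAP 9.1.1 tabulates. Repeat events in one visit count once, which softens the ratios. For illustration, take a constant Poisson rate of 3.16 events over the 729 days, so P = 1 − exp(−3.16 × days/729):

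- Month 3: 1 − exp(−0.585) = 0.443, or about 665 of 1500
- Month 6: 1 − exp(−0.394) = 0.326, or about 489
- Month 24: 1 − exp(−0.204) = 0.184, or about 276

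The ratios to Month 6 are 0.443/0.326 = 1.36 and 0.184/0.326 = 0.56 (0.565 unrounded). Month 3/Month 24 is about 2.4. The 3.16 is the baseline hazard in Protocol 7.7, to which that section then applies covariate effects. It is the rate with covariates at zero, not a forecast for this cohort.

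**Share dated between visits.** Let a share q of escalations be dated between visits and the rest be dated at visits, evenly across them. The event ratio is then q × r + (1 − q), with r = 1.48 or 0.52. The documents do not give q, so these values are assumptions:

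| q | Month 3/Month 6 | Month 24/Month 6 | Month 3/Month 24 |
|---|---|---|---|
| 100% | 1.48 | 0.52 | 2.9 |
| 50% | 1.24 | 0.76 | 1.6 |
| 20% | 1.10 | 0.90 | 1.2 |

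**Comparison.** Counting each escalation in the interval that ends at the next target day gives 90, 91, 91, 92, 91, 91, 91 and 92 days.

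**The case against.** The strongest reply is that little rests on this table. The study asks which factors drive escalation, and the Cox model answers that. Because the model leaves the baseline hazard free, uneven catchment alone need not bias its hazard ratios. Timing by actual date is already planned: time to first escalation (SAP 7.1.2.1) and drug survival (SAP 7.1.2.10) use recorded dates with Kaplan-Meier methods. Therapy is documented at quarterly visits, so many switches may be dated at a visit, where the rule does little. The table shells are in a separate document that we have not seen. All of this stands, and it confines the point to a descriptive display. It does not remove the unequal catchment from that display, which carries the timing part of the primary endpoint. The sensitivity analysis that assigns switches to the prior visit is specified for the model, and the SAP does not say that the table will be rebuilt from it.

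The nearest-visit sentence is also loosely worded and might mean attended visits, in which case the day counts would vary by patient. The tie rule, which measures distance from the escalation date, supports the reading used here.

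A reader might also infer that the rule contradicts the endpoint definition, under which an escalation "is defined as a switch to another DMARD or combination of DMARDs when compared to the last visit". A switch on day 120 would first be seen at Month 6 yet is counted at Month 3. That is not a true conflict. The wording defines what counts as a switch, not where it is tabulated, and a day-120 switch qualifies under either placement.

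**Conclusion.** The point holds for the by-time-point table of the primary endpoint. Following the SAP exactly, the table would show a spurious high at Month 3 and, if observation ends by about day 758, a spurious low at Month 24 under a constant escalation rate. The upper bound for event counts is 1.48 and 0.52 times Month 6, with all escalations spread evenly and observation ending on day 730. For people with an event, the illustrative figures are about 1.36 and 0.56. Both shrink towards 1 as fewer escalations are dated between visits.

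Three stronger readings are not supported. The rule does not create a decline over 24 months: Months 6 to 21 are flat, so the artefact is one step at each end. It does not by itself invalidate the regression or the date-based time-to-event results. And multiplying 1500 patients by 3.16 does not predict the table, because SAP 9.1.1 counts people and 3.16 is not an expected rate.

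The sponsor should correct this before the final tables are produced. It is a reporting matter and does not threaten the main inference.

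**What to change.** For the by-time-point escalation tables only, count each escalation by its recorded date in consecutive intervals between target days: 2–91, 92–182, 183–273, 274–365, 366–456, 457–547, 548–638, and 639 to the end of observation, up to day 758. Days 2 to 45 then fall in the first interval without a transfer from baseline, and days 92 to 136 move from Month 3 to Month 6. Keep the exclusion of switches before first tofacitinib.

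Use patients under observation at the start of each interval as the denominator. Also report escalations per patient-time at risk: the last interval is 92 days if it ends on day 730 and 120 if it ends on day 758, and only a rate makes it comparable with the others.

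The cost is SAP wording and a small programming change. No new data are needed, because Protocol 7.6.5 already collects stop and start dates at each escalation. The downside is that these tables would no longer share the visit windows of the secondary endpoints, which the sponsor aligned on purpose. The windows for those endpoints stay as they are.
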